Appendix 3 Pharmacokinetics, Immunogenicity, and Pharmacodynamic Biomarkers Schedule

Cycle	Day	Time Points	Windows	PK ^a	ADA ^a	Cytokines	PD Biomarker ^{a,b}	Serum Biomarker ^{a,b}	Fc Gamma Receptor Genotyping
Cycle 1	1	Pre retifanlimab or tebotelimab infusion	n/a	X	X	X	X	X	X
		End of retifanlimab or tebotelimab infusion	+15 min	X					
		Pre enoblituzumab infusion ^c	n/a	X					
		End of enoblituzumab infusion	+15 min	X		X	X	X	
		4 hours after end of enoblituzumab infusion	±10 min	X		X		X	
	2	No specific time	n/a	X		X	X	X	
	3	No specific time	n/a	X		X	X	X	
	8	No specific time	n/a	X		X	X	X	
15	No specific time	n/a	X		X	X	X		
Cycle 2 Odd Cycles ≥3	1	Pre retifanlimab or tebotelimab infusion	n/a	X	X	X	X	X	
		End of retifanlimab or tebotelimab infusion	+15 min	X					
		Pre enoblituzumab infusion ^c	n/a	X					
		End of enoblituzumab infusion	+15 min	X		X	X	X	
Cycle 4 Cycle 6	1	Pre retifanlimab or tebotelimab infusion	n/a	X	X		X	X	
		End of retifanlimab or tebotelimab infusion	+15 min	X					
		Pre enoblituzumab infusion ^c	n/a	X					
		End of enoblituzumab infusion	+15 min	X					
IRR-CRS ^d	n/a	No specific time	n/a	X		X			
End of Treatment ^e	n/a	No specific time	n/a	X	X		X	X	
Follow-up	n/a	12 weeks after end of treatment ^f	n/a	X	X				
	n/a	24 weeks after end of treatment ^f	n/a	X	X				

a Do not collect PK, ADA, or biomarker samples from the infusion port. Blood samples will be collected from the arm contralateral to the site of IV infusion. If an indwelling catheter is used, the fluid in the catheter will be removed and discarded prior to the collection of blood sample for PK, ADA, or biomarker assessments. Obtain PK samples as follows: Pre-infusion: Before start of first infusion on visit day (dosing day). When collecting multiple samples, collect the PK sample first.

b PD biomarker and serum biomarker samples to be collected only up to and including Cycle 6.

c Only to be collected if enoblituzumab is not administered on the same day as retifanlimab or tebotelimab.

d Additional samples may be obtained selectively at additional time points in patients who experience signs and symptoms of infusion related reaction or cytokine release syndrome.

e Sample to be collected at EOTV or, if no EOTV is conducted, when the decision is made to end treatment.

f For patients with evidence of ADA from any prior visit. End of treatment refers to EOTV or, if no EOTV is conducted, when the decision is made to end treatment.

Cycle	Day	Time Points	Windows	PK ^a	ADA ^a	Cytokines	PD Biomarker ^{a,b}	Serum Biomarker ^{a,b}	Fc Gamma Receptor Genotyping
-------	-----	-------------	---------	-----------------	------------------	-----------	-----------------------------	--------------------------------	------------------------------

Notes:

- Actual start and end of infusion times, PK, and ADA sample collection times will be recorded on the CRFs.
- Pre-infusion samples should be collected before the start of infusion on visit day (dosing day).
- End of infusion (EOI) is defined in the Pharmacy Manual.
- Samples required at EOI can be drawn up to 15 minutes after the infusion is complete. For each study drug, up to 10 additional minutes of infusion time are permitted to allow for flushing the line:
 - Retifanlimab infusion duration = 60 minutes.
 - Tebotelimab infusion duration = 60 minutes.
 - Enoblituzumab infusion duration = 120 minutes.

Appendix 4 RECIST 1.1 Guidelines

Adapted from Eisenhauer 2009 (32).

All patients will be required to have at least 1 measurable lesion to be considered as having measurable disease at baseline for the determination of eligibility for this study. Measurable lesions are defined below.

1 Measurability of Tumor at Baseline

1.1 Definitions

At baseline, tumor lesions/lymph nodes will be categorized measurable or non-measurable as follows:

1.1.1 Measurable

Tumor lesions: Must be accurately measured in at least one dimension (*longest* diameter in the plane of measurement is to be recorded) with a *minimum* size of:

- 10 mm by CT scan (CT scan slice thickness no greater than 5 mm).
- 10 mm caliper measurement by clinical exam (lesions which cannot be accurately measured with calipers should be recorded as non-measurable).
- 20 mm by chest X-ray.

Malignant lymph nodes: To be considered pathologically enlarged and measurable, a lymph node must be ≥ 15 mm in *short* axis when assessed by CT scan (CT scan slice thickness recommended to be no greater than 5 mm). At baseline and in follow-up, only the *short* axis will be measured and followed. See also notes below on ‘Baseline documentation of target and non-target lesions’ for information on lymph node measurement.

1.1.2 Non-measurable

All other lesions, including small lesions (longest diameter < 10 mm or pathological lymph nodes with ≥ 10 to < 15 mm short axis) as well as truly non-measurable lesions. Lesions considered truly non-measurable include leptomeningeal disease, ascites, pleural or pericardial effusion, inflammatory breast disease, lymphangitic involvement of skin or lung, abdominal masses/abdominal organomegaly identified by physical exam that is not measurable by reproducible imaging techniques.

1.1.3 Special considerations regarding lesion measurability

Bone lesions, cystic lesions, and lesions previously treated with local therapy require particular comment:

Bone lesions:

- Bone scan, PET scan or plain films are not considered adequate imaging techniques to measure bone lesions. However, these techniques can be used to confirm the presence or disappearance of bone lesions.
- Lytic bone lesions or mixed lytic-blastic lesions, *with identifiable soft tissue components*, that can be evaluated by cross sectional imaging techniques such as CT or MRI can be considered as measurable lesions if the *soft tissue component* meets the definition of measurability described above.
- Blastic bone lesions are non-measurable.

Cystic lesions:

- Lesions that meet the criteria for radiographically defined simple cysts should not be considered as malignant lesions (neither measurable nor non-measurable) since they are, by definition, simple cysts.
- ‘Cystic lesions’ thought to represent cystic metastases can be considered as measurable lesions, if they meet the definition of measurability described above. However, if non-cystic lesions are present in the same patient, these are preferred for selection as target lesions.

Lesions with prior local treatment:

- Tumor lesions situated in a previously irradiated area, or in an area subjected to other loco-regional therapy, are not considered measurable unless there has been demonstrated progression in the lesion prior to study enrollment.

1.2 Specifications by methods of measurements

1.2.1 Measurement of lesions

All measurements should be recorded in metric notation, using calipers if clinically assessed. All baseline evaluations should be performed as close as possible to the treatment start and never more than 4 weeks before the beginning of the treatment.

1.2.2 Method of assessment

The same method of assessment and the same technique should be used to characterize each identified and reported lesion at baseline and during follow-up. Imaging based evaluation should always be done rather than clinical examination unless the lesions(s) being followed cannot be imaged but are assessable by clinical exam.

Clinical lesions: Clinical lesions will only be considered measurable when they are superficial and ≥ 10 mm diameter as assessed using calipers (e.g. skin nodules). For the case of skin lesions, documentation by color photography including a ruler to estimate the size of the lesion is suggested. As noted above, when lesions can be evaluated by both clinical exam and imaging, imaging evaluation should be undertaken since it is more objective and may also be reviewed at the end of the study.

Chest X-ray: Chest CT is preferred over chest X-ray, particularly when progression is an important endpoint, since CT is more sensitive than X-ray, particularly in identifying new lesions. However, lesions on chest X-ray may be considered measurable if they are clearly defined and surrounded by aerated lung.

CT, MRI: CT is the best currently available and reproducible method to measure lesions selected for response assessment. This guideline has defined measurability of lesions on CT scan based on the assumption that CT slice thickness is 5 mm or less. When CT scans have slice thickness greater than 5 mm, the minimum size for a measurable lesion should be twice the slice thickness. MRI is also acceptable in certain situations (e.g., for body scans).

Ultrasound: Ultrasound is not useful in assessment of lesion size and should not be used as a method of measurement. Ultrasound examinations cannot be reproduced in their entirety for independent review at a later date and, because they are operator dependent, it cannot be guaranteed that the same technique and measurements will be taken from one assessment to the next. If new lesions are identified by ultrasound in the course of the study, confirmation by CT or MRI is advised. If there is concern about radiation exposure at CT, MRI may be used instead of CT in selected instances.

Endoscopy, laparoscopy: The utilization of these techniques for objective tumor evaluation is not advised.

Tumor markers: Tumor markers *alone* cannot be used to assess *objective* tumor response.

2 Tumor Response Evaluation

2.1 Assessment of overall tumor burden and measurable disease

To assess objective response or future progression, it is necessary to estimate the *overall tumor burden at baseline* and use this as a comparator for subsequent measurements. Only patients with measurable disease at baseline should be included. Measurable disease is defined by the presence of at least one measurable lesion (as detailed above).

2.2 Baseline documentation of ‘target’ and ‘non-target’ lesions

Where more than one measurable lesion is present at baseline all lesions up to a maximum of five lesions total (and a maximum of two lesions per organ) representative of all involved organs should be identified as *target lesions* and will be recorded and measured at baseline. For example, in instances where patients have only one or two organ sites involved, a maximum of two and four lesions respectively will be recorded). Target lesions should be selected on the basis of their size (lesions with the longest diameter), be representative of all involved organs, but in addition should be those that lend themselves to *reproducible repeated measurements*. It may be the case that, on occasion, the largest lesion does not lend itself to reproducible measurement in which circumstance the next largest lesions which can be measured reproducibly should be selected.

Lymph nodes merit special mention since they are normal anatomical structures which may be visible by imaging even if not involved by tumor. As noted above, pathological nodes which are defined as measurable and may be identified as target lesions must meet criterion of a short axis of ≥ 15 mm by CT scan. Only the *short* axis of these nodes will contribute to the baseline sum. The short axis of the node is the diameter normally used by radiologists to judge if a node is involved by solid tumor. Nodal size is normally reported as two dimensions in the plane in which the image is obtained (for CT scan this is almost always the axial plane; for MRI the plane of acquisition may be axial, sagittal or coronal). The smaller of these measures is the short axis. For example, an abdominal node which is reported as being 20 mm x30 mm has a short axis of 20 mm and qualifies as a malignant, measurable node. In this example, 20 mm should be recorded as the node measurement. All other pathological nodes (those with short axis ≥ 10 mm but < 15 mm) should be considered non-target lesions. Nodes that have a short axis < 10 mm are considered non-pathological and should not be recorded or followed.

A *sum of the diameters* (longest for non-nodal lesions, short axis for nodal lesions) for all target lesions will be calculated and reported as the *baseline sum diameters*. If lymph nodes are to be included in the sum, then as noted above, only the *short* axis is added into the sum. The baseline sum diameters will be used as reference to further characterize any objective tumor regression in the measurable dimension of the disease.

All other lesions (or sites of disease) including pathological lymph nodes should be identified as *non-target lesions* and should also be recorded at baseline. Measurements are not required and these lesions should be followed as ‘present’, ‘absent’, or in rare cases ‘unequivocal progression. In addition, it is possible to record multiple non-target lesions involving the same organ as a single item on the case record form (e.g. ‘multiple enlarged pelvic lymph nodes’ or ‘multiple liver metastases’).

2.3 Response criteria

This section provides the definitions of the criteria used to determine objective tumor response for target lesions.

2.3.1 Evaluation of target lesions

Complete Response (CR): Disappearance of all target lesions. Any pathological lymph nodes (whether target or non-target) must have reduction in short axis to < 10 mm.

Partial Response (PR): at least a 30% decrease in the sum of diameters of target lesions, taking as reference the baseline sum diameters.

Progressive Disease (PD): at least a 20% increase in the sum of diameters of target lesions, taking as reference the *smallest sum on study* (this includes the baseline sum if that is the smallest on study). In addition to the relative increase of 20%, the sum must also demonstrate an absolute increase of at least 5 mm. (*Note*: the appearance of one or more new lesions is also considered progression).

Stable Disease (SD): Neither sufficient shrinkage to qualify for PR nor sufficient increase to qualify for PD, taking as reference the smallest sum diameters while on study.

2.3.2 Special notes on the assessment of target lesions

Lymph nodes. Lymph nodes identified as target lesions should always have the actual short axis measurement recorded (measured in the same anatomical plane as the baseline examination), even if the nodes regress to below 10 mm on study. This means that when lymph nodes are included as target lesions, the ‘sum’ of lesions may not be zero even if complete response criteria are met, since a normal lymph node is defined as having a short axis of < 10 mm. In order to qualify for CR, each node must achieve a short axis < 10 mm. For PR, SD and PD, the actual short axis measurement of the nodes is to be included in the sum of target lesions.

Target lesions that become ‘too small to measure’. While on study, all lesions (nodal and non-nodal) recorded at baseline should have their actual measurements recorded at each subsequent evaluation, even when very small (e.g. 2 mm). However, sometimes lesions or lymph nodes which are recorded as target lesions at baseline become so faint on CT scan that the radiologist may not feel comfortable assigning an exact measure and may report them as being ‘too small to measure’. When this occurs it is important that a value be recorded on the case report form. If it is the opinion of the radiologist that the lesion has likely disappeared, the measurement should be recorded as 0 mm. If the lesion is believed to be present and is faintly seen but too small to measure, a default value of 5 mm should be assigned (*Note*: It is less likely that this rule will be used for lymph nodes since they usually have a definable size when normal and are frequently surrounded by fat such as in the retroperitoneum; however, if a lymph node is believed to be present and is faintly seen but too small to measure, a default value of 5 mm should be assigned in this circumstance as well). This default value is derived from the 5 mm CT slice thickness (but should not be changed with varying CT slice thickness). The measurement of these lesions is potentially non-reproducible, therefore providing this default value will prevent false responses or progressions based upon measurement error. However, if the radiologist is able to provide an actual measure, that should be recorded, even if it is below 5 mm.

Lesions that split or coalesce on treatment. When non-nodal lesions ‘fragment’, the longest diameters of the fragmented portions should be added together to calculate the target lesion sum. Similarly, as lesions coalesce, a plane between them may be maintained that would aid in obtaining maximal diameter measurements of each individual lesions. If the lesions have truly coalesced such that they are no longer separable, the vector of the longest diameter in this instance should be the maximal longest diameter for the ‘coalesced lesion’.

2.3.3 Evaluation of non-target lesions

This section provides the definitions of the criteria used to determine the tumor response for the group of non-target lesions. While some non-target lesions may actually be measurable, they need not be measured and instead should be assessed only *qualitatively* at the time points specified in the protocol.

Complete Response (CR): Disappearance of all non-target lesions. All lymph nodes must be non-pathological in size (< 10 mm short axis).

Non-CR/Non-PD: Persistence of one or more non-target lesions(s).

Progressive Disease (PD): *Unequivocal progression* (see comments below) of existing non-target lesions. (*Note*: the appearance of one or more new lesions is also considered progression).

2.3.4 Special notes on assessment of progression of non-target disease

The concept of progression of non-target disease requires additional explanation as follows:

When a patient also has measurable disease. In this setting, to achieve ‘unequivocal progression’ on the basis of the non-target disease, there must be an overall level of substantial worsening in non-target disease such that, even in presence of SD or PR in target disease, the overall tumor burden has increased sufficiently to merit discontinuation of therapy. A modest ‘increase’ in the size of one or more non-target lesions is usually not sufficient to qualify for unequivocal progression status. The designation of overall progression *solely* on the basis of change in non-target disease in the face of SD or PR of target disease will therefore be extremely rare.

When the patient has only non-measurable disease. The same general concepts apply here as noted above, *however*, in this instance there is no measurable disease assessment to factor into the interpretation of an increase in non-measurable disease burden. Because worsening in non-target disease cannot be easily quantified (by definition: if all lesions are truly non-measurable) a useful test that can be applied when assessing patients for unequivocal progression is to consider if the increase in overall disease burden based on the change in non-measurable disease is comparable in magnitude to the increase that would be required to declare PD for measurable disease: i.e. an increase in tumor burden representing an additional 73% increase in ‘volume’ (which is equivalent to a 20% increase diameter in a measurable lesion). Examples include an increase in a pleural effusion from ‘trace’ to ‘large’, an increase in lymphangitic disease from localized to widespread, or may be described in protocols as ‘sufficient to require a change in therapy’. If ‘unequivocal progression’ is seen, the patient should be considered to have had overall PD at that point. While it would be ideal to have objective criteria to apply to non-measurable disease, the very nature of that disease makes it impossible to do so; therefore, the increase must be substantial.

2.3.5 New Lesions

The appearance of new malignant lesions denotes disease progression. There are no specific criteria for the identification of new radiographic lesions; however, the finding of a new lesion should be unequivocal: i.e. not attributable to differences in scanning technique, change in imaging modality or findings thought to represent something other than tumor (for example, some ‘new’ bone lesions may be simply healing or flare of pre-existing lesions). This is particularly important when the patient’s baseline lesions show partial or complete response. For example, necrosis of a liver lesion may be reported on a CT scan report as a ‘new’ cystic lesion, which it is not.

A lesion identified on a follow-up study in an anatomical location that was *not* scanned at baseline is considered a new lesion and will indicate disease progression. An example of this is the patient who has visceral disease at baseline and while on study has a CT or MRI brain

ordered which reveals metastases. The patient's brain metastases are considered to be evidence of PD even if he/she did not have brain imaging at baseline.

If a new lesion is equivocal, for example because of its small size, continued therapy and follow-up evaluation will clarify if it represents truly new disease. If repeat scans confirm there is definitely a new lesion, then progression should be declared using the date of the initial scan.

2.4 Evaluation of best overall response

The best overall response is the best response recorded from the start of the study treatment until the end of treatment taking into account any requirement for confirmation. The patient's best overall response assignment will depend on the findings of both target and non-target disease and will also take into consideration the appearance of new lesions.

2.4.1 Time point response

It is assumed that at each protocol specified time point, a response assessment occurs. [Table A-1](#) on the next page provides a summary of the overall response status calculation at each time point for patients who have measurable disease at baseline.

2.4.2 Missing assessments and inevaluable designation

When no imaging/measurement is done at all at a particular time point, the patient is not evaluable (NE) at that time point. If only a subset of lesion measurements is made at an assessment, usually the case is also considered NE at that time point, unless a convincing argument can be made that the contribution of the individual missing lesion(s) would not change the assigned time point response. This would be most likely to happen in the case of PD. For example, if a patient had a baseline sum of 50 mm with three measured lesions and at follow-up only two lesions were assessed, but those gave a sum of 80 mm, the patient will have achieved PD status, regardless of the contribution of the missing lesion.

2.4.3 Best overall response: all time points

The *best overall response* is determined once all the data for the patient is known.

Table A-1 Time point response: patients with target (+/- non-target) disease

Target lesions	Non-target lesions	New lesions	Overall response
CR	CR	No	CR
CR	Non-CR/non-PD	No	PR
CR	Not evaluated	No	PR
PR	Non-PD or not all evaluated	No	PR
SD	Non-PD or not all evaluated	No	SD
Not all evaluated	Non-PD	No	NE
PD	Any	Yes or No	PD
Any	PD	Yes or No	PD
Any	Any	Yes	PD

CR = complete response, PR = partial response, SD = stable disease, PD = progressive disease, and NE = inevaluable.

Best response determination in trials where confirmation of complete or partial response IS required: Complete or partial responses may be claimed only if the objective response is confirmed on a follow-up scan obtained no less than 4 weeks after the initial scan demonstrating an objective response. In this circumstance, the best overall response can be interpreted as in **Table A-2**.

Table A-2 Best overall response when confirmation of CR and PR required

Overall response First time point	Overall response Subsequent time point	BEST overall response
CR	CR	CR
CR	PR	SD, PD or PR ^a
CR	SD	SD
CR	PD	SD
CR	NE	SD
PR	CR	PR
PR	PR	PR
PR	SD	SD
PR	PD	SD provided minimum criteria for SD duration met, otherwise, PD
PR	NE	SD provided minimum criteria for SD duration met, otherwise, NE
NE	NE	NE

CR = complete response, PR = partial response, SD = stable disease, PD = progressive disease, and NE = inevaluable.

- a. If a CR is *truly* met at first time point, then any disease seen at a subsequent time point, even disease meeting PR criteria relative to baseline, makes the disease PD at that point (since disease must have reappeared after CR). Best response would depend on whether minimum duration for SD was met. However, sometimes ‘CR’ may be claimed when subsequent scans suggest small lesions were likely still present and in fact the patient had PR, not CR at the first time point. Under these circumstances, the original CR should be changed to PR and the best response is PR.

Special notes on response assessment

When nodal disease is included in the sum of target lesions and the nodes decrease to ‘normal’ size (< 10 mm), they may still have a measurement reported on scans. This measurement should be recorded even though the nodes are normal in order not to overstate progression should it be based on increase in size of the nodes. As noted earlier, this means that patients with CR may not have a total sum of ‘zero’ on the case report form (CRF).

Patients with a global deterioration of health status requiring discontinuation of treatment without objective evidence of disease progression at that time should be reported as ‘symptomatic deterioration’. Every effort should be made to document objective progression even after discontinuation of treatment. Symptomatic deterioration is *not* a descriptor of an objective response: it is a reason for stopping study therapy. The objective response status of such patients is to be determined by evaluation of target and non-target disease as shown in [Table A-1](#) and [Table A-2](#).

For equivocal findings of progression (e.g., very small and uncertain new lesions; cystic changes or necrosis in existing lesions), treatment may continue until the next scheduled assessment. If at

the next scheduled assessment, progression is confirmed, the date of progression should be the earlier date when progression was suspected.

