14 STATISTICAL ANALYSIS

This section outlines the statistical methodology and principles which will be used for data analysis in this study. A separate statistical analysis plan (SAP) and statistical programming plan (SPP) will further describe the details regarding statistical methods and will govern the analysis.

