5 ENDPOINTS

5.1 Efficacy Endpoints

5.1.1 Primary Efficacy Endpoints

The primary efficacy endpoint is the Investigator-assessed ORR per Response Evaluation Criteria in Solid Tumours version 1.1 (RECIST v1.1), defined as the proportion of patients in the response evaluable population who achieve the best overall response (BOR) of complete response (CR) or partial response (PR) (called responders) per RECIST v1.1. The BOR will be categorized as CR, PR, stable disease (SD), progressive disease (PD), or not evaluable (NE). To be qualified as an objective response, CR and PR require confirmation at least 4 weeks after initial observation of such response, and SD requires an observation at least once after 6 weeks. BOR will be evaluated from the start of study treatment.

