5.1.2 Secondary Efficacy Endpoints

The secondary efficacy endpoints are:

- PFS assessed by Investigator, defined as the time from the first dose date to the date of first documented progression or death from any cause, whichever occurs first. The documented progression is determined by objective assessment of disease per RECIST v1.1. For patients who are not known to be dead or progressed at time of data cut-off for PFS analysis, the PFS will be censored at the date of the last tumor assessment. Specifically, the following censoring rules will be applied ([Table 2](#)).
 - $\text{PFS (months)} = (\text{date of event [documented progression or death] or date of censoring} - \text{date of first dose} + 1) / (365.25/12)$

Table 2 Censoring Rules for PFS Analysis

Situation	Date	Outcome
No baseline tumor assessments	First dose date	Censored
Death prior to first scheduled tumor assessment	Date of death	Progressed
No post-baseline tumor assessments in absence of death prior to first scheduled tumor assessment	First dose date	Censored
Documented progression	Date of progression	Progressed
Initiation of alternative anti-cancer treatments in absence of documented progression	Date of last tumor assessment prior to initiation of such treatment	Censored
Death or documented progression immediately after missing 2 or more consecutive scheduled tumor assessments	Date of last tumor assessment prior to missed assessments	Censored

- DoR, defined as the time from the date of initial response (CR or PR) to the date of first documented progression per RECIST v1.1 or death from any cause, whichever occurs first. The DoR is calculated only for the responders. For responders who are not known to be dead or progressed at the time of data cut-off for DoR analysis, the DoR will be censored at the date of the last tumor assessment. Specifically, the last 3 situations described in **Table 2** will be applied. The DoR analyses will be performed only if there are enough responders to render the analyses meaningful.
 - $\text{DoR (months)} = (\text{date of event [documented progression or death] or date of censoring} - \text{date of initial response} + 1) / (365.25/12)$
- DCR, defined as the percentage of response evaluable patients who experienced response of CR, PR, or SD for at least 3 months.

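### Table A-2 gives an unconfirmed CR followed by PD or NE a best response of SD with no minimum duration, unlike the matching PR rows, footnote a and the 6-week SD rule

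*Protocol*

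**What the plan says.** Protocol 11.1.1 refers BOR to RECIST v1.1 as set out in Appendix 4. Table A-2 there classifies pairs of scans when CR and PR must be confirmed. PR then PD is "SD provided minimum criteria for SD duration met, otherwise, PD" and PR then NE is "SD provided minimum criteria for SD duration met, otherwise, NE". CR then SD, CR then PD and CR then NE are each SD with no condition. PR then SD is also SD with no condition.

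Footnote a is marked only on the CR-then-PR row. It says that after a true CR, "any disease seen at a subsequent time point, even disease meeting PR criteria relative to baseline, makes the disease PD at that point", and it continues: "Best response would depend on whether minimum duration for SD was met". It also allows for a CR that was really a PR, in which case the first reading is corrected to PR.

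SAP 5.1.1 sets a minimum for SD: "SD requires an observation at least once after 6 weeks". Protocol 14.6.1 has the same rule. SAP 5.1.2 gives the related secondary endpoint: "DCR, defined as the percentage of response evaluable patients who experienced response of CR, PR, or SD for at least 3 months". Protocol section 14 says that the SAP and the statistical programming plan (SPP) "will further describe the details regarding statistical methods and will govern the analysis".

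**The concern.** Nothing in the documents explains why the minimum SD duration should apply when the unconfirmed first reading is PR but be waived when it is CR. Footnote a, by its wording, covers any disease after a true CR, so it covers CR then PD, and that row leaves out the condition the footnote states.

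The BOR breakdown is reported with the primary endpoint (SAP 6.7.1), and SD feeds the disease control rate (DCR). A patient who progressed at the second scan, or had no evaluable scan after the first, could be listed as SD only because the first reading was CR. The error would always run in favour of treatment, since PD or NE becomes SD.

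**Working it through.** The plan states no figure on this point to reproduce. The check compares the rows, then asks whether the scan schedule lets the difference matter.

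**1. Rows of Table A-2 side by side**

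| Second scan | First scan CR | First scan PR | Same? |
|---|---|---|---|
| SD | SD | SD | yes |
| PD | SD | SD if minimum met, else PD | no |
| NE | SD | SD if minimum met, else NE | no |

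The CR and PR rows differ for PD and NE only. CR then SD conflicts with footnote a (disease is still visible after a true CR), not with its PR counterpart. Footnote a does not reach CR then NE, because no disease is seen there. That row conflicts with PR then NE and with the 6-week rule.

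**2. Scan timing**

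Inputs: scans at the end of Cycle 2 (window -3 days) and then every 3 cycles (window -7 days), from Protocol 11.1.1; cycle length 21 ± 3 days with at least 18 days between doses, from Protocol Appendix 1. Days after first dose = cycles × interval, minus 0 up to the window.

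| Interval | First scan | Second scan |
|---|---|---|
| 18 days | 2×18 = 36, to 33 | 5×18 = 90, to 83 |
| 21 days | 2×21 = 42, to 39 | 5×21 = 105, to 98 |
| 24 days | 2×24 = 48, to 45 | 5×24 = 120, to 113 |

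Six weeks is 42 days. At 21-day cycles, a first scan on days 39 to 41 precedes 6 weeks and one on day 42 is on the boundary. At 18-day cycles every first scan is early. At 24-day cycles none is.

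**3. DCR**

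Appendix 4 section 2.5.3 measures SD from start of treatment to progression. Three months is 3 × 365.25/12 = 91.3 days. I assume the SAP's convention for its other durations (add 1 day, divide by 365.25/12). At 21-day cycles the second scan is then at (98+1)/30.44 = 3.25 to (105+1)/30.44 = 3.48 months, long enough to count. At 18-day cycles it is at (83+1)/30.44 = 2.76 to (90+1)/30.44 = 2.99 months, too short.

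**4. Example records**

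- CR on day 40, PD on day 105. Literal CR row: SD, and in DCR. PR-row wording: PD, and not in DCR.
- CR on day 40, no later evaluable scan. Literal CR row: SD. PR-row wording: NE. Only about 6 weeks of control was observed, so DCR changes only if duration is run past the last evaluable scan.
- CR on day 46, then PD or NE. SD under either wording.

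**5. Size per affected patient**

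1/50 = 2.0 points in the Retifanlimab Cohort and 1/30 = 3.3 points in the Tebotelimab Cohort, on the SD versus PD/NE split. ORR changes by 0, because an unconfirmed CR is not a responder.

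**The case against.** The strongest reply is that the minimum is already set. Protocol 14.6.1 and SAP 5.1.1 apply the 6-week rule to SD without exception, and the SAP and SPP govern. Table A-2 sits in an appendix of guidelines and is introduced permissively, and footnote a states the duration condition. The SPP, which will hold the programming specifications, is not among the documents. A careful programmer could therefore reach the right answer.

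Much of this stands. A reader might infer that BOR and DCR are miscounted. The documents show only that they can be, if the table is programmed literally against the general rule. The reply is not complete, however. The SAP gives no rule for sequences of scans, Protocol 11.1.1 sends BOR to Appendix 4, and Table A-2 is the only such rule in the two documents. Two programmers could classify the same patient differently.

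On timing, a reader might infer that the first scan never meets the minimum. That is not so: 24-day intervals and the dose delays of up to 20 days in Protocol 4.3.1 can carry it past 6 weeks. With Study Day 1 as the first dosing day (SAP 6.1), a scan 42 days after first dose is Study Day 43, which some would accept.

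On DCR, a patient who progresses at day 105 was free of documented progression for more than 3 months, so counting disease control is arguable. But the answer should not depend on whether the unconfirmed first reading was CR or PR.

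**Conclusion.** The inconsistency is real and minor. The CR-then-PD and CR-then-NE cells lack the minimum-duration condition of the matching PR cells and conflict with the 6-week rule. Footnote a contradicts the CR-then-PD cell and, by its wording, the CR-then-SD cell.

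It would be tempting to say that all three CR rows are treated more leniently than the PR rows. Table A-2 does not support that, because PR then SD is unconditional too.

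The results change only when a first-scan CR is unconfirmed, that scan fails the 6-week minimum, and the table is coded literally. A DCR effect is essentially limited to CR then PD (or, through footnote a, CR then SD) at about days 98 to 105. The documents give no rate for such records. If 2 to 6% of patients read CR at the first scan and 10 to 30% of those were not confirmed (both assumptions), the count would be 80 × 0.02 × 0.10 = 0.16 to 80 × 0.06 × 0.30 = 1.44 of 80 patients. That range is too high for the affected group, since it includes records that both wordings classify alike.

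ORR, the 14/50 criterion and the 3/30 criterion do not change, and DCR has no threshold. One caveat: this rests on the table's extracted text. The longer PR cells are intact there, so lost wording in the CR cells is unlikely, but the cells should be checked on the page.

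**What to change.** In Table A-2, change the CR-then-PD cell to "SD provided minimum criteria for SD duration met, otherwise, PD" and the CR-then-NE cell to "SD provided minimum criteria for SD duration met, otherwise, NE", matching the PR rows. Mark footnote a on the CR-then-SD row as well. That edit rests on the footnote alone, since PR then SD carries no condition to match. State in the SAP or SPP that the 6-week minimum applies to every BOR of SD, say whether a scan exactly 42 days after first dose meets it, and program BOR accordingly.

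The cost is two table cells, one footnote mark, a sentence in the SAP or SPP, and the matching lines of the BOR program. The downside is that an occasional SD becomes PD or NE.
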